STUDY PROTOCOL

THE EFFICACY AND SAFETY OF FIRST LINE ANTI-EPILEPTIC DRUGS (AEDs) AS SUBSTITUTION THERAPY FOR CHILDREN WITH DRUG RESISTANT EPILEPSY

Protocol Number 22-09-1097

ABSTRACT

Background: Drug resistant epilepsy occurs around 30% of children with epilepsy. It is the failure to get seizure-free after combining two or more anti-epileptic drugs whether first- or second-line ones. Previous studies focus on the efficacy and safety between the two groups whether as add-on or substitution therapy mostly in newly diagnosed epilepsy children. However, the study that investigate first line Anti-epileptic Drugs (AEDs) as substitution therapy compared to second-line ones particularly among drug resistant epilepsy children is still lack. **Design**: It is an open-label, randomized controlled trial, which will be conducted in three referral hospitals in Jakarta, Cipto Mangunkusumo, Harapan Kita, and Fatmawati Hospital, from November 2022 until April 2023. The data will be collected from electronic medical record consisting of demographic, clinical characteristics, and brain CT scan or brain MRI, and diary cards that record daily drug consumption and adverse drug reaction. Self-administered QOLCE-55 questionnaire is used to assess the quality of life of the children. Furthermore, there will be EEG and laboratory examination prior and after intervention. The data will be recorded on Case Report Form that is filled by the researcher. Ethics committee approval is obtained from The Ethics Committee of The Faculty of Medicine, University of Indonesia-Cipto Mangunkusumo Hospital. Research permits would be issued by each institution where the study will take place.

Sample: There will be 100 participants, divided into 2 groups, the intervention and control. Fifty children in the intervention group will be treated with first line AEDs as the substitution therapy, while the other 50 participants in the control group will get second-line AEDs. The sample size is calculated based on the difference proportion of two independent groups.

Duration of the study: The study will take 14 weeks as a whole that consists of 6 phases including baseline, initial, titration, maintenance, tapering-of, stopping and another maintenance phase.

Introduction

older agents. On the other hand, topiramate, levetiracetam, oxcarbazepine are newer agents that are taken frequently for the second-line AEDs. 12, 13 The American Academy of Neurology (AAN) subcommittee reports in 2004 observed that newer AEDs were not different in controlling seizures but have better tolerability, particularly fewer neurotoxic adverse effect.¹⁴-¹⁶ There have been many studies comparing the efficacy and safety between first and secondline AEDs in newly diagnosed epilepsy children, showed that first-line agents are as efficacious as second ones. Guerreiro reported that seizure freedom rate in childhood absence epilepsy treated with phenytoin did not differ from those with oxcarbazepine.¹⁷ A study in Turki explained valproic acid, carbamazepine and phenobarbital have the same efficacy as levetiracetam for newly diagnosed epilepsy children. 18 The results was in line with that was reported by James, that valproic acid, carbamazepine as first-line agents and topiramate as the second one are equally effective to treat newly diagnosed epilepsy children. 19 While for drugresistant epilepsy, previous research investigated that children did not get seizure-free although they have been treated with levetiracetam, known as second-line AED, as add-on therapy.²⁰ However, there is no robust evidence for therapeutic efficacy of first-line AEDs as substitution of second-line ones. When it comes guideline therapy, there has not been any international guideline of combination therapy for the management of drug resistant epilepsy, even though many recommendations that have been made regionally in certain countries.

In the local situation in Indonesia where the study will be conducted, there are some challenges in the management of drug-resistant epilepsy in children. Similar to those in other countries, a study at Cipto Mangunkusumo General Hospital, Jakarta, showed that around 43% and 31% did not get seizure remission children although they have been given topiramate or levetiracetam respectively. Besides, from the factual situation at outpatient pediatric neurology clinic in Jakarta, the capitol of Indonesia, the number of the drugs that were covered by social insurance are limited so that sometimes patients should buy themselves the uncovered drugs that are needed. Moreover, the newer agents are sometimes not available even in the referral hospitals in other cities spreading all over the country.

Randomized studies in drug-resistant epilepsy typically involve addition of new anti-epileptic drugs. However, in clinical practice, if the patient is already taking multiple drugs, then substitution of one of the current medications commonly occurs, despite little evidence supporting this approach.²² The choice of the substitution drug depends on the mechanism of action, the pharmacokinetic profile, drug-drug interaction, and the risk of seizure exacerbation as well as patients-related factors. The new combination is intended to maximize efficacy and minimize toxicity. However, the availability and cost-effectiveness should also be

taken into consideration since the patient would not reach the goal of ideal combination of drugs if they could not afford it nor even get the medication. ²³⁻²⁶ Another considerable case is one of drug resistance patterns in which at the first-time patients may not responsive to treatment yet they change into a state that is responsive to the medication. ²⁷ The choice of substitution therapy may originate from firs-line AEDs since evidences have shown they have equal efficacy to those of second-line ones. However, there is still lack of evidence whether the drug resistance pattern occur if the substitution drug is originated from first-line AED even more if it has ever been given prior to the current drug combination. ²⁷ The study aims to analyzed the efficacy and safety of first-line AEDs as substitution therapy in drug-resistant epilepsy children.

Primary Objective

The primary outcome of the research is to analyze the proportion of responders, who are defined as subjects who get 50% of seizure reduction.

Secondary Objectives

There are some secondary objectives of the study. The first one is to analyze the differences of improvement of quality of life, EEG feature and time to achieve seizure reduction, between the intervention and the control group. Besides, the research will describe the clinical characteristics, adverse effects of the drugs and laboratory features related to the adverse effects, among children with drug-resistant epilepsy. Furthermore, it will explain factors influencing the reduction of seizure frequency

Study Design

This protocol is intended for a multicenter open label experimental, randomized controlled trial on the efficacy and safety of using first line AEDs as substitution therapy in childhood drug-resistant epilepsy. It will prospectively follow 100 children up during 14 weeks that consist of baseline, intervention, and post-intervention phases. While the intervention consists of 6 steps, as described at the Figure 1 below.

[figure not shown]

Figure 1. Timeline of the intervention phases

The study will be conducted at pediatric outpatient clinic of 3 referral hospitals in Jakarta, Cipto Mangunkusumo Hospital, Harapan Kita Hospital and Fatmawati Hospital. Children who are diagnosed with drug-resistant epilepsy receiving levetiracetam or topiramate will be enrolled in the study. Enrollment begins as soon as the research ethics committee approval is obtained from The Ethics Committee of The Faculty of Medicine, University of Indonesia-Cipto Mangunkusumo Hospital. The study will be closed after the last recruited patient has been followed up for the required 14 weeks.

All recruited children will be examined for monitoring at the hospital where the intervention is initiated. To avoid selection bias, all patients who met the inclusion criteria are divided into two groups, the intervention and control groups. Prospective participants and their parents will be provided with information related to the study. Patients will then fill out an information sheet containing demographic data, comorbidities, developmental history, school history, history of drug consumption, as well as history of seizures and patient complaints. All the data will be extracted and recorded on the case report form. Patients and their parents should be informed that participation is voluntary and they are free to withdraw from the study at any time. They should also be informed that refusal to participate or withdraw from the study will not affect the quality of treatment received. In the event of their withdrawal, it will be explained that the data collected so far is irrevocable, and we will seek consent to use such data in the final analysis if necessary.

Study procedure

Study procedures are depicted in Figure 2. The patients who are eligible for the study and have given their consents, will be enrolled, divided into 2 groups, the intervention and control, then start the 3-day baseline phase. In this phase, data such as demographic, clinical characteristic

including seizure frequency, seizure type, seizure onset, medication history, family history of seizure, and also developmental stages, will be recorded from electronic medical record. Besides, the CT-scan or MRI are also collected from the same source. After that, their quality of life will be assessed by QOLCE-55 validated questionnaire through self-guided report. Furthermore, the laboratory investigation and EEG will be performed.

The next phase is intervention phase, started from initial step and ended by the maintenance of new combination therapy, which takes with overall 12 weeks. Initially, the substitution drugs with each initial dose are consumed. The drugs consist of valproic acid for the generalized and carbamazepine for focal epilepsies. On the other hand, the control group will take lamotrigine or clobazam for generalized and oxcarbazepine for focal ones. The phase continuous to titration dose, in which, the dose is raised gradually until it causes 50% of seizure reduction, and the next step is maintained the dose for about 2 weeks.

The following is tapering-off and after that stopping the substituted drug, levetiracetam or topiramate, which is determined by considering individual condition. Yet, if the seizures increase more than one and a half time of the previous frequency during the phases, the intervention will be ended immediately. On the contrary, if the condition is better, then the children go to the maintenance of new combination, that is the substitution drug and the old drugs in which the seizures do not go up or even better keep going down. The children who complete all of the phases are categorized as responder. In case if the intervention is ended, the subjects will be given the former combination therapy with adjusted doses in order to decrease the seizures until reaching the pre-intervention condition. The subjects are categorized as non-responder, and will be dropped-out. The other criteria of drop-out are resignation, non-compliance of study procedure, and death in term of other causal not related to the study. While in term of lost to follow-up, is intended for those who do not attend the study without any possible reasons.

[figure not shown]

Figure 2. flow-chart of the study

Maintenance the dose of the new combination therapy that consist of the new drug and

Maintenance

old drug after stopping the substituted drug

Inclusion criteria

- 1. Children age at 1 18 years old
- 2. Children diagnosed as drug-resistant epilepsy by pediatric neurologists, diagnosis was based on the ILAE 2017 criteria
- 3. Children will have got at least 3 months of combination therapy that consists of levetiracetam of topiramate with optimal of therapeutic dosages

Exclusion criteria

- 1. Non-convulsive epilepsy
- 2. Suffered from status epilepticus in the prior 3 months before the study begins
- 3. Past medical history of idiosyncrasies or severe adverse drug reactions caused by the substitution therapy that will be given

Instrument of the study

QOLCE-55 questionnaire

Once the children are enrolled, quality of life will be assessed by using validated QOLCE-55 questionnaire. It is parent-reported and self-administered questionnaire which assess quality of life children with epilepsy age 4-18 years of age. The researcher will give a detail explanation about filling the questionnaire. It has 55 questions including cognitive (22 items), emotional (17 items), social (7 items) and also physical (9 items) function. Items are rated on a five-point Likert scale, 0 = very often, 1 = fairly often, 2 = sometime, 3 = almost never, 5 = never. The composite score is the unweighted average of the four subscales, ranging from 1-100, higher score indicates better quality of life.²⁸

Diary Card

The other important thing to evaluate is subjects' adherence, seizure frequencies, and adverse drug reaction by self-reported diary card which is filled by the parents each day during the intervention phase. Besides, drug consumption compliance is also assessed by counting the tablets or powder packages during routine visits of the study.

Electronic Medical Record

Electronic Medical Record is used to collect secondary data that include demographic data, clinical characteristic, and imaging such as brain-CT or brain-MRI.

Laboratory Examination

The test is performed in hospitals' laboratory where the study take place and is done twice, at the baseline and post intervention phase. The order of the blood test consists of complete blood test, liver function test including alanine and aspartate transaminase, kidney function test including urea and creatinine, and also blood electrolyte that consist of natrium, kalium and calcium. The laboratory professional takes the blood from vein of the arm. The subjects are seated or lying down, accompanied by the parents, while for the younger children, they seat on his/her parents' lap or position that make them feel comfortable. Older children may be asked to make a fist and then will be tied by a rubber band around his/her arms. After that, the needle is inserted the needle until the blood is drawn. The laboratory worker will take the needle since the amount of blood is enough and puts an adhesive bandage over the site. The next step is analyzes of the sample and the result will be issued for about 1-2 days both printed or provided on the electronic medical record.

Electroencephalography Examination

The EEG examination is operated two times, at the baseline and post intervention phase, with high density machine (Caldwell Easy III) is done twice, pre- and post-intervention. The machine will operate for about 45 minutes including 5 minutes each for eye-open and eye-close in every subjects. Beginning with acquisition, EEG recordings use standard parameter to analyze brain activity at various frequencies to gain good quality and artefact-free result. The printed results of the EEG is available for about 4-7 days after the examination.

Data collection

All relevant data will be recorded, by nominated member(s) of the research team, on a case report form (CRF). Each participant will have a CRF and be assigned a unique identification number.

Baseline data

At entry into the study, the following baseline information will be recorded in the CRF:

- unique patient identification number contact telephone number and/or email address
- date of entry into the study
- eligibility for study entry based on inclusion/exclusion criteria
- age at study entry, in years and months
- gender
- weight and height
- seizure type (eg, generalized tonic clonic, absence, myoclonic and partial)
- the age at diagnosis and duration of epilepsy
- seizure frequency or average number of seizures per month
- current anticonvulsant(s) with doses and formulation and its side effect (if presents)
- other medications and its side effect (if presents)

- first recognized seizure date
- prior EEG and laboratory which has been performed at the baseline phase
- physical examination

Follow-up data

Follow-up data will be collected during regularly scheduled clinic visits (per 2 weeks). This information will be obtained from the participants' diary card. Important information to be collected at follow-up will include:

- physical examination
- adverse drug reaction of the substitution therapy that happen
- seizure's frequency
- type of seizure
- complaint

Outcome evaluation

- a. The difference in responders was the difference in the percentage of responders in the group that used first line OAE again as substitution therapy and those that used standard therapy. Responders are subjects who experience a decrease frequency of seizure more than or equal to 50% of the initial seizure. Frequency of seizure is the number of seizures that occur within 1 month. In previous studies, it was said that the frequency of seizures was said to have decreased significantly or was said to respond if the seizures were reduced by 50% or more from the initial seizure. ^{19, 29} Based on this, researchers will categorize the frequency of seizures into:
 - Responder: there is a decrease in the frequency of seizures by 50% or more than before
 - Non-responder: namely the frequency of seizures remains or decreases but not up to 50% of the initial seizure frequency or the frequency is more than before

Furthermore, the proportion in the form of the percentage of respondents in the two groups is calculated and differentiated, therefore it is classified into two groups:

- Different : when a significant difference is shown in difference of proportion test of the 2 unpaired groups.
- Not different: when there is no significant difference is shown in difference of proportion test of the 2 unpaired groups.

- b. Differences in quality of life: quality of life assessment using QOLCE-55 instrument. The average of each function (cognitive, emotional, social and physical functions) and the average of the total functions are assessed. This variable is categorized into:
 - Different, if there is a difference in the average quality of life
 - Not different, if there is no difference in the average quality of life
- c. Differences in electroencephalography appearance

EEG recording results are categorized into:

- Normal: does not show of hypofunction/asymmetry/epileptiform waves
- Abnormal: shows a picture of hypofunction/asymmetry/epileptiform waves or a combination of 1 or more of these features

The subjects who show changes in their EEG are later grouped into groups of abnormal to normal or abnormalities that showed improvement. Abnormalities that show improvement, for example are hypofunction (slowing down) waves experience improvement or decreasing number of epileptiform waves.

Next, a proportion calculation is carried out in the form of the percentage to subjects who experience a change in the EEG and will be categorized into:

- Different : when a significant difference is shown in difference of proportion test of the group that reuses first line OAE line as substitution therapy and those that use standard therapy/
- Not different: when there is no significant difference is shown in difference of proportion test of the 2 groups.
- d. Difference in actual failure between the groups reusing first line OAE as substitution therapy and those taking standard therapy. Description of drug side effects in the form of frequency distribution and percentage of side effects in each group. Description of laboratory results in the form of frequency distribution and percentage of side effects in each group
- e. Factors contributing to decrease in seizure frequency (age, seizure onset, seizure type, family history of seizures, developmental delay, history of OAE, initial seizure frequency, initial EEG, structural brain abnormalities)

Sample size

The estimated sample size in this study was calculated using the different proportion formula for the 2 unpaired groups as follows ²⁹:

$$n1 = n2 = (\frac{Z_{\alpha}\sqrt{2PQ} + Z_{\beta}\sqrt{P1Q1 + P2Q2}}{P1 - P2})^{2}$$

Description:

n1 number of subjects who received the new drug (First Line OAE)

n2 number of subjects receiving standard drug (Second line OAE)

Alpha type one error (5%)

Zα alpha standard value 5% one-way hypothesis (1,96)

Beta type two error (20%)

Zβ beta default value 20% (0,84)

P2 proportion of decreased seizures on standard drugs (reference) for example 0.7

Q2
$$1-P2 = 1-0.7 = 0.3$$

P1-P2 difference in the proportion of reduced seizure that is considered significant between the new drug and the standard (defined by the researcher) for example 25% (0.25)

P1 proportion of reduced seizure on the new drug (the proportion of reduced seizure on the standard drug in addition to the minimal difference that is considered significant)= 0.7 + 0.25 = 0.95

Q1
$$1 - P1 = 1 - 0.95 = 0.5$$

P
$$(P1 + P2) / 2 = (0.95 + 0.7) / 2 = 0.825$$

Q
$$1-P = 1-0.825 = 0.175$$

In this study, it was found that the proportion of seizure reduction on standard drugs was 70%.³⁰ Therefore the equation:

$$n1 = n2 = \left(\frac{1,96\sqrt{2(0,825)(0,175)} + 0,84\sqrt{(0,95)(0,5) + (0,7)(0,3)}}{0,25}\right)^2 = 49,56 = 50$$

$$n\ 2\ groups=100$$

Based on the formula above, 100 research subjects are required. An additional of 10% from the total number of subjects are needed as there is a possibility of those dropping out, therefore a total of 110 subjects are needed in this study.

Statistical Analysis

- 1. Analysis of differences in the proportion of responders (primary outcome), differences in EEG appearance (secondary outcome) in pediatric epilepsy patients who are resistant to the combination of second line OAE between those who reused first line OAE as substitution therapy and those who used standard therapy. Data type is categorical. Data is analyzed the Chi-square statistical test, if it does not meet the requirements then an alternative test is performed, known as Fisher's multiple test. The significance level (α) is 5% and the research confidence level is 80%. If p value ≤ α is obtained, this means H0 is rejected, which means that there is a difference seen in seizure frequency between reusing first line OAE as substitution therapy and standard therapy.
- 2. Analysis of differences in the mean quality of life with an unpaired T test if the data distribution is normal or Mann-Whitney if data distribution is not normal
- 3. To assess drug effectiveness, the analysis used was the difference in actual failure between those using first line OAE as substitution therapy and those using standard therapy (primary outcome). Formula:

$$ARR = CER - EER$$

CER: the incidence of increased seizure frequency in the standard therapy group ERR: the incidence of increased seizure frequency in the group in substitution therapy with 1st line OAE The increase in seizure frequency in this study shows therapy

This test will use 2 analyses known as intention to treat analysis and per-protocol analysis. Intention to treat analysis means that all research subjects who have been randomized are included in the analysis according to their initial allocation regardless of whether or not the subject is taking the drug/therapy being tested or a placebo, or whether these subjects died before taking the drug being tested. Subjects who did not

failure.

take medication, lost to follow-up, and who moved to another group, are considered failures of their original group.

Whereas per protocol analysis only includes subjects who complete the research to the end.

- 4. Analysis of the difference in time to achieve a decrease in seizure frequency with the chisquare test or if it does not meet the requirements, an alternative test is performed, namely the Mann-Whitney test
- 5. Analysis of clinical characteristics, side effects of OAE, and laboratory findings of complete blood count (hemoglobin, hematocrit, leukocytes, platelets, and type count), liver function (SGOT and SGPT), kidney function (urea and creatinine), and blood electrolytes (sodium, potassium, calcium, chloride) in pediatric epilepsy patients who are resistant to combination second OAE who re-use first line OAE as substitution therapy and who use standard therapy (secondary outcome). All existing data is processed and presented in a table consisting of mean and standard deviation or median and inter-quartile range, as well as frequency distribution.
- 6. Analyzing factors that affect the decrease in the frequency of late seizures (age, seizure onset, seizure type, family history of seizures, developmental delays, history of OAE, initial seizure frequency, initial EEG, brain structural abnormalities) in pediatric patients with resistant epilepsy combination of second line OAE who re-use first line OAE as substitution therapy (secondary outcome).

Data is categorical. Data is analyzed using Chi-square statistical test, if results do not meet the requirements then an alternative test will be performed, known as Fisher's multivariate test and further analyzed with multivariate test and logistic regression analysis. The significance level (α) is 5% and the research confidence level is 80%. Results will show statistically related if value of $p \le \alpha$ is obtained.

Ethics and dissemination

The study will only be initiated after the protocol, consent form and the participants' information sheet are approved by The Ethics Committee of The Faculty of Medicine, Indonseia University-Cipto Mangunkusumo Hospital. We also apply for research permits at the 3 hospitals where the research will he held.

Informed Consent

Written informed consent will be obtained from the parents of participants. A potential participant whose more than 12 year-old at the time of clinic appointment will be given an informed assent. The writer will explain the details of the study and provide age-appropriate

participant information sheet to the participants and their parents. All questions about the study will be answered by the writer. Participants will be allowed sufficient time to decide whether to participate in the study or not. Before enrollment, the consent form will be signed by parents, or also by the participant who are 12 years old or above. If either the children or their parent decline to consent, they will not enter the study. The participant or their parent will keep a copy of the consent form, while the original copy will be kept by the chief writer in the recruitment file, a third copy will be kept in the patient's hospital record.

Discontinuation of study participation

Participants may choose to withdraw from the study, on their own or on the request of their parents/guardian, at any time during the course of the study. Subjects may withdraw for any reason without prejudice to his/her future medical care by the physician or at the institution. On withdrawal of consent, the date and reason for consent withdrawal will be documented. Participants' data collected up to the date of the withdrawal of consent may be included in the final analysis.

The investigator may also choose to withdraw a participant from the study if such a person does not comply with the procedure, did not participate in the study at least until the standard drug tapering-off phase, or died during the study. Withdrawn participants will not be replaced.

Study Records and Data Management

- Case report form

Each participant will be assigned a unique study patient identification number, for use on CRFs, other study documents, and the electronic database. CRFs will be treated as confidential documents. The writer will make a separate confidential record of the participant's name, date of birth, local hospital number and patient identification number to permit identification of all participants enrolled in the study, in case additional follow-up is required.

CRFs shall be restricted for approved personnel by the chief investigator only. All paper forms shall be filled in using black ballpoint pen. Errors shall be lined out but not obliterated by using correction fluid and the correction inserted, initially and dated. Personnel who fill in the CRF must affix their identity in the form of name and signature

- Record retention and archiving

The chief investigator will retain all records and documents for 5 years. If the responsible investigator can no longer retain these records, another person will be nominated for this purpose.

The final archiving of the study documents and databases (and associated metaencryption codes) held by the chief investigator shall be at the secure archive facility at the University of Indonesia.

- Publication and dissemination policy

Participants will not be paid to participate in the study. However, they will be given transportation costs. There will be no hospital visits in excess of usual care. Findings will be published in peer-reviewed journals.

References

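### Children are divided into arms before the baseline phase of an open-label trial, so the baseline QOLCE-55, the EEG reading and the extraction of seizure frequency can be made with the arm known

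*Combined protocol and SAP*

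**What the plan says.** The Study procedure section gives the order: eligible, consenting patients "will be enrolled, divided into 2 groups, the intervention and control, then start the 3-day baseline phase". It then lists the work of that phase. Clinical history, including seizure frequency, is taken from the electronic medical record. Next, "their quality of life will be assessed by QOLCE-55 validated questionnaire through self-guided report", followed by laboratory tests and EEG. The substitution drug starts in the phase after that.

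The Study Design section calls the trial a "multicenter open label experimental, randomized controlled trial". The available text describes no allocation concealment, no later disclosure of the arm, no masked data extractor and no masked EEG reader.

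Under Baseline data, the CRF item is "seizure frequency or average number of seizures per month". Outcome evaluation, item a, defines the primary endpoint against it: "Responders are subjects who experience a decrease frequency of seizure more than or equal to 50% of the initial seizure". The same item counts frequency over 1 month. The Diary Card paragraph confines the parents' daily diary to the intervention phase.

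**The concern.** A responder is defined by a ratio of later to initial seizure frequency. If knowledge of the arm affects the recorded initial value, the responder rate in that arm moves without any treatment effect, and no later analysis can separate the two.

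Two secondary outcomes also rest on baseline. The Secondary Objectives refer to improvement in quality of life, and Outcome evaluation, item c, grades EEG change from the first recording. A parent who knows the arm may score the first QOLCE-55 differently, and an EEG reader who knows it may grade the first tracing differently. In an open-label trial the follow-up data cannot be fully protected, but the baseline can be, if it is finished before anyone knows the arm.

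**Working it through.** The plan gives no figure on this point, so there is none to reproduce. The check is a reading of the sequence, then an illustration of scale.

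**Sequence, item by item**

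| Baseline item | When | Who produces it | What knowledge of the arm could affect |
|---|---|---|---|
| QOLCE-55 | Baseline phase, after division into groups | Parent, unmasked | The answers themselves |
| EEG | Same phase | Reader, no masking described | The grading, not the recording |
| Monthly seizure frequency | Same phase | Extracted from the medical record; the researcher fills in the CRF | Which period is used and how entries are averaged, not the entries |

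The third row needs one more step. The baseline phase lasts 3 days and the diary starts only with the intervention, so a monthly frequency cannot be counted prospectively. It must be retrospective. The text fixes no reference month and no averaging window, which leaves a judgement to be made after allocation.

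**Scale, for illustration only**

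From the Sample size section: a responder proportion of 0.70 on standard drugs and 50 children per group. Assumed, and not in the documents: no true difference between arms; the log of the follow-up/baseline ratio is normal with SD *s* = 0.5, 0.8 or 1.0; recorded baseline is multiplied by *f* in one arm only.

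A child counts as a responder when follow-up/(*f* × baseline) ≤ 0.5, so the rate in the shifted arm is

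Φ( z(0.70) + ln *f* / *s* ), with z(0.70) = 0.524.

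Example: *f* = 1.1 and *s* = 0.5 give Φ(0.524 + 0.0953/0.5) = Φ(0.715) = 0.763.

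The last column is the exact probability that a two-sided 5% chi-square test rejects when this rate is compared with 0.70, at 50 per arm.

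| Shift *f* | *s* | Responder rate, shifted arm | Chance of a significant result |
|---|---|---|---|
| 1.0 (none) | any | 70.0% | 5.0% |
| 1.1 | 0.5 | 76.3% | 10.9% |
| 1.1 | 0.8 | 74.0% | 7.3% |
| 1.1 | 1.0 | 73.2% | 6.5% |
| 1.2 | 0.5 | 81.3% | 26.2% |
| 1.2 | 0.8 | 77.4% | 13.5% |
| 1.2 | 1.0 | 76.0% | 10.4% |

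The no-shift row belongs in the range, because record-based extraction may introduce no shift at all. Nothing in the documents indicates which arm would be favoured.

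**The case against.** The strongest reply is that the primary denominator is the least exposed baseline item. It comes from the medical record, and what was written before allocation cannot depend on the arm. This stands. It limits the concern for seizure frequency to selection and averaging, and makes a 10-20% one-arm shift hard to justify as an expectation. It does not touch QOLCE-55.

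Three stronger readings are tempting, and the documents do not support them.

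- *The family's seizure history is given after allocation.* In Study Design the division into groups is mentioned before the sentence "Patients will then fill out an information sheet containing demographic data". But that sentence directly follows one about giving information to prospective participants, and its time word most naturally refers to that step. The paragraph is not a timeline: read as one, it would put allocation before families are informed, against the order in Study procedure.
- *Every baseline value is obtained with the arm known.* No sentence says when the arm is disclosed. Knowledge at baseline is inferred from the open-label design, the stated order and the absence of any masking. Figure 2 is not available here and might add detail.
- *A child who leaves between allocation and baseline cannot be classified.* Statistical Analysis, item 3, counts randomised children who take no medication or are lost to follow-up as failures of their original group, so no denominator is needed for them.

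It is also fair to say that QOLCE-55 and EEG are done before the substitution drug, so they remain pre-treatment measures, and that the unmasked follow-up diary is a more direct exposure which reordering leaves untouched. Both are true. Neither is a reason to leave the baseline open as well, when protecting it takes only a change of order.

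**Conclusion.** The point holds in limited form. The text places division into arms before the baseline phase of an open-label trial and describes neither delayed disclosure nor masked assessment. Baseline QOLCE-55, the EEG reading and the extraction of seizure frequency can therefore be made with the arm known. The exposure is direct for QOLCE-55, depends on an unmasked reader for EEG, and for the primary denominator is confined to extraction, averaging and choice of reference period.

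The order of procedures is explicit; that the arm is known at baseline is an inference. The size of any bias cannot be found from the documents. The tabulated rejection rates of 6.5-26.2% rest wholly on assumed shifts of 10-20% and assumed SDs, and show only how sensitive the endpoint would be if a shift occurred.

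**What to change.** Change the sequence in Study procedure, and in Figure 2 if it shows the same order. After consent, complete the record extraction, QOLCE-55, EEG and laboratory tests. Enter the baseline monthly seizure frequency on the CRF and lock it. Only then make or reveal the allocation, before the first dose of the substitution drug. If the sponsor already intends to disclose the arm later, the text should say so.

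The cost is a delay of about 3 days before allocation. The plan expects printed EEG results about 4-7 days after the examination, so allocation would wait longer if the reading itself must come first; a reader who is not told the arm avoids that wait. No extra tests are needed. The documents do not say whether allocation and baseline share a visit. If they do, some rescheduling may be needed, and it should be checked against the statement under Publication and dissemination policy that hospital visits will not exceed usual care.
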